	APPENDIX A: IMPUTATION OF PARTIALLY UNKNOWN ADVERSE EVENT DATES25					
	PENDIX B: DEFINITION OF THE TERM "TREATMENT-EMERGENT" WITH RESPECT TO A					
AT I	CLASSIFICATION					

LIST OF ABBREVIATIONS

AE adverse event

ATA antitherapeutic antibodies
ASCT autologous stem cell transplant

AUC area under the concentration-time curve C_{coi} concentration at the end of infusion

C_{max} maximum concentration
C_{trough} trough concentration
CI confidence interval
CR complete remission
CSR clinical study report
DLT dose-limiting toxicity
ECG electrocardiogram

ECOG eastern cooperative oncology group

EOT end of treatment

eCRF electronic case report form
HL Hodgkin lymphoma
IHC immunohistochemistry
IRR infusion related reaction
IPI international prognostic index

MedDRA medical dictionary for regulatory activities

MMAE monomethyl auristatin E

NCI CTCAE national cancer institute common terminology criteria for adverse events

ORR objective response rate

OS overall survival
PD progressive disease

PD-1 programmed cell death protein 1

PFS progression-free survival

PK pharmacokinetics
PN peripheral neuropathy
PR partial remission
SAE serious adverse event
SAP statistical analysis plan
SMC safety monitoring committee

SPD sum of the products of the largest diameter T_{max} time at which the maximum concentration occurs

WHO world health organization

1 INTRODUCTION

This document outlines the statistical methods to be implemented within the scope of Protocol SGN35-025, entitled 'A phase 1/2 study evaluating brentuximab vedotin in combination with nivolumab in patients with relapsed or refractory Hodgkin lymphoma after failure of frontline therapy'. Results of the proposed analyses will become the basis of the clinical study report for this protocol.

The purpose of this plan is to provide specific guidelines from which the analysis will proceed. All planned analyses specified in this document will be performed. Any changes to this plan, in the form of "post hoc" or "data driven" analyses will be identified as such in the final clinical study report. Any changes will either be reflected in amendments to this plan before the database lock or specifically documented in the clinical study report.

2 STUDY OBJECTIVES

2.1 Primary Objectives

- To assess the safety profile of brentuximab vedotin administered in combination with nivolumab in patients with relapsed or refractory HL
- To assess the antitumor activity of brentuximab vedotin administered in combination with nivolumab in patients with relapsed or refractory HL

2.2 Secondary Objectives

- To assess the objective response rate (ORR)
- To assess the duration of complete remission (CR) and objective response (OR)
- To assess progression-free survival (PFS) after autologous stem cell transplant (ASCT)

2.3 Additional Objectives

- To assess overall survival (OS)
- To compare the CR rate in patients who relapsed after frontline therapy with the CR rate in patients who were refractory to frontline therapy
- To assess the feasibility of stem cell mobilization and collection after treatment with brentuximab vedotin in combination with nivolumab
- To assess PFS
- To assess pharmacokinetics and antitherapeutic antibody (ATA) incidence of each study drug given in combination
- To assess tumor amplification and expression of PD-L1/L2 and relationship to response
- To assess tumor microenvironment and peripheral immune status

3 STUDY ENDPOINTS

3.1 Primary Endpoints

- Type, incidence, severity, seriousness, and relatedness of adverse events and laboratory abnormalities
- Complete remission rate following the completion of study treatment

3.2 Secondary Endpoints

- Objective response rate
- Duration of CR and OR
- Progression-free survival post-ASCT

3.3 Additional Endpoints

- Overall survival
- PFS
- Selected PK, ATA, and biomarker endpoints

4 STUDY DESIGN

This is a phase 1/2, open-label, multicenter study designed to evaluate the safety and antitumor activity of brentuximab vedotin treatment combined with nivolumab in patients with relapsed or refractory Hodgkin lymphoma after failure of frontline therapy.

Part 1 of the study will evaluate safety of possible dosing regimens for the combination treatment prior to expansion of enrollment. Following completion of Part 1, Part 2 and 3 of the study will further evaluate safety and efficacy of the combination treatment.

The safety of combination treatment in Part 1 will be evaluated by a Safety Monitoring Committee (SMC) prior to expansion of enrollment in Part 2 to evaluate treatment effect. In Part 1, after 6 patients have been followed through the end of the dose-limiting toxicity (DLT) period, or at the point that 2 or more patients experience a DLT, whichever comes first, the SMC will review all available data and make a recommendation for one of the following:

- 1. To proceed to Part 2 of the study, expanding enrollment with approximately 50 additional patients treated with the study drugs at the doses and schedule determined to be safe in Part 1 of the study
- 2. To repeat Part 1 of the study and treat up to 6 additional patients, possibly with a modified dosing regimen
- 3. To close the study to further enrollment

Following completion of enrollment of Part 1 and Part 2, the study was amended to add Part 3. Approximately 30 additional patients will be enrolled for Part 3.

Patients will be treated for up to four 21-day cycles. Unless subsequently modified based on planned SMC review, treatment will be administered as described in this paragraph. In Parts 1 and 2, the first dose of brentuximab vedotin 1.8 mg/kg will be given on Cycle 1 Day 1. The first dose of nivolumab 3 mg/kg will be given on Cycle 1 Day 8. For Cycle 2 and all subsequent cycles, brentuximab vedotin 1.8 mg/kg followed by nivolumab 3 mg/kg will be given on Day 1. In Part 3, both brentuximab vedotin 1.8 mg/kg and nivolumab 3 mg/kg will be administered on Day 1 of all Cycles. For patients in Part 3 who were previously treated with brentuximab vedotin and had a dose reduction, dose assignment must be discussed with the medical monitor.

Lymphoma response and progression will be assessed by investigators using the Lugano Classification Revised Staging System for malignant lymphoma (Cheson 2014). CT scans (chest, neck, abdomen, and pelvis) and PET scans will be performed at baseline, at the End of Treatment (EOT), pre-ASCT, and during long-term follow-up; PET is performed with CT scans until the patient is in complete metabolic response (CmR) by PET. Pre-ASCT scans may be waived for patients who had an EOT scan performed within 6 weeks prior. CT scans of diagnostic quality will be performed at Cycle 2 to assess for progression of disease. Long-term follow-up assessments will be performed at the following time points post-ASCT (or for patients who do not undergo ASCT, post-EOT): 100 days and then 6, 9, 12, 18, 24, 30, and 36 months, and then per institutional standard thereafter. A final safety visit will be performed 100 days after the last dose of nivolumab or at EOT (whichever is later) to assess for potential immune-mediated adverse events. Patients will be followed at this schedule until withdrawal of consent, death, or study closure, whichever occurs first.

For Part 3 response assessments were modified to inclue the Lymphoma Response to Immunomodulatory Therapy Criteria (LYRIC), which allows for an assessment of indeterminate response in cases where apparent progression may be due to the immunomodulatory effects of the treatment and not due to true disease progression.

5 ANALYSIS SETS

This section defines each of the analysis sets that will be utilized. The use of each analysis set will be discussed in Section 7.

5.1 All Enrolled Patients Analysis Set

The All Enrolled Patients analysis set includes all patients enrolled in the study. The All Enrolled Patients set will be used for the primary efficacy analysis. Secondary and additional efficacy endpoints will also be analyzed using this analysis set. Patients will be analyzed according to the dose regimen to which they were enrolled.

5.2 All Treated Patients Analysis Set

The All Treated Patients analysis set includes all patients who receive any amount of brentuximab vedotin or nivolumab. The All Treated Patients set will be used for presentation of safety data and may be used for exploratory analyses of efficacy endpoints.

5.3 Efficacy Evaluable (EE) Analysis Set

The Efficacy Evaluable analysis set includes all patients who had an adequate baseline disease assessment, received any amount of either drug, and subsequently had an adequate response assessment. The Efficacy Evaluable set will be used for exploratory analysis of efficacy endpoints. Patients will be analyzed according to actual dose regimen received.

6 STATISTICAL CONSIDERATIONS

6.1 General Principles

This is a phase 1/2 open label study with a formal statistical hypothesis for the primary efficacy endpoint of CR rate. The test of the primary endpoint will be at level $\alpha = 0.05$, using a 1-sided test. There are no formal pre-specified hypotheses associated with the primary safety objective, and no additional hypothesis tests of secondary endpoints.

Descriptive statistics (mean, median, standard deviation, minimum, maximum) will be used to describe continuous variables. Frequencies and percentages will be used to describe categorical variables. The median survival time will be estimated using the Kaplan-Meier method; the associated confidence interval (CI) will be calculated based on the complementary log-log transformation (Collett 1994). Unless otherwise specified, confidence intervals will be calculated at a two-sided 95% level.

Patients will be summarized overall and by dose regimen, unless otherwise specified in section 7. Additional summaries may be performed by selected patient characteristics and for subgroups of interest.

Any analysis not described in this plan will be considered exploratory, and will be documented in the clinical study report (CSR) as a post hoc analysis or a change to the planned analysis.

To comply with regulatory electronic submission guidelines, listings of all clinical data will be submitted as electronic data sets. To facilitate data review for the study report, only pertinent data listings will be created and attached to the appendix of the CSR. All statistical output will be produced using SAS®, version 9.4 or more recent. Other statistical software, if used, will be described in the CSR.

6.2 Determination of Sample Size

It is anticipated that a total of approximately 55 patients will be enrolled in this study in parts 1 and 2. For Part 3 approximately 30 patients will be enrolled. This number for Part 1 and 2 was chosen in order to enable an adequately powered analysis of the primary endpoint of CR rate and to characterize the safety profile of the combination treatment. This number will be

greater if multiple dose regimens are investigated in Part 1 of the study as only those patients from Part 1 who are treated with the dose regimen chosen for Part 2 will be included in the analysis of the primary endpoint.

The sample size needed to provide adequate power to test the primary endpoint is at least 53. With this sample size, if the true CR rate is 50%, a one-sided exact binomial test at level α =0.05 will reject the null hypothesis of a CR rate less than or equal to 30% approximately 90% of the time. For the given parameters the null hypothesis will be rejected when 22 or more CRs are observed (i.e., CR rate \geq 41.5% is observed).

For Part 3, no formal hypothesis test is specified. The sample size of 30 patients was chosen to allow adequate precision of estimates for response rates and safety data. For example, if 63% (19/30) of patients have a CR, then the 95% exact CI is (44%, 80%). The sample size of 30 patients is sufficient to perform exploratory biomarker analyses.

For the safety assessment of the combination treatment, a sample size of 55 patients will provide a 94% chance of observing at least one occurrence of an adverse event with a true event rate of 5%.

East 5.4 was used to perform sample size calculations.

6.3 Randomization and Blinding

No randomization will be carried out and no blinding will be enforced as this is an open label trial.

6.4 Data Transformations and Derivations

No data transformations are planned for the primary endpoints.

Reported age in years will be used; if not available, age in years will be calculated with the SAS INTCK function (with method specified as "continuous") using informed consent date and birth date.

Study Day will be calculated as (Date - First Dose Date + 1) for dates on or after the first dose date. For dates prior to the first dose date, Study Day will be calculated as (Date - First Dose Date). For all calculations of Study Day, the First Dose Date will be the earliest date of treatment administration for any study drug.

Other time variables based on two dates, e.g., Start Date and End Date, will be calculated as (End Date - Start Date + 1) (in days) unless otherwise specified in the planned analysis section.

The following unit conversion will be implemented unless otherwise specified:

Months = Days / 30.4375

Years = Days / 365.25

Baseline values used in all analyses will be the most recent non-missing measurement prior to the first dose of study drug.

The end-of-treatment (EOT) date will be the date the EOT visit is performed; if an EOT visit is not performed then the EOT date will be either the EOS date or 30 days after the last dose of any study drug, whichever is earlier.

For efficacy assessments, the date of response will be the latest of all radiologic scan dates for the given restage assessment. The date of progression will be the earliest of all radiologic scan dates for the given restage assessment, or the date of investigator claim of clinical progression. An adequate tumor assessment to determine response must include a radiologic(CT) scan and a PET scan. Determination of progression by radiologic assessment may be based on CT or PET alone if there is clear evidence of PD by one of these modalities. While a radiologic assessment to confirm progression is strongly preferred, an investigator claim of clinical progression is adequate for an assessment of PD.

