## 7.2 Response/Efficacy Assessments

### 7.2.1 Parts 1 and 2

For patients in Parts 1 and 2, the determination of antitumor activity will be based on response assessments made according to the Lugano Classification Revised Staging System for malignant lymphoma ([Cheson 2014](#)) and treatment decisions by the investigator will be based on these assessments.

Staging will be performed by PET and CT of diagnostic quality, with disease involvement determined by focal fluorodeoxyglucose (FDG) uptake in nodal and extranodal sites (including spleen, liver, bone marrow, and thyroid) that is consistent with lymphoma, according to the pattern of uptake and/or CT characteristics. Up to six of the largest nodes, nodal masses, or other involved lesions that are measurable in two diameters should be identified as target lesions; if possible they should be from disparate regions of the body, and they should include mediastinal and retroperitoneal areas of disease whenever these sites are involved.

At Cycle 2 (Day 15 + 6 days), a CT scan of diagnostic quality will be performed to assess for PD; a limited scan that includes sites of disease identified at baseline is acceptable. For subsequent response assessments, both PET and CT scans will be required until the patient achieves a CmR by PET assessment. After the patient achieves a CmR by PET, response will be followed by CT scans of diagnostic quality only. For PET-based assessments, a clinical response of progressive metabolic disease (PmD), no metabolic response (NmR), partial metabolic response (PmR), or CmR will be determined. If only CT-based assessment is performed, response will be categorized as PD, SD, PR, or CR. PmD/PD includes radiological evidence of progression per Lugano Classification Revised Staging System for malignant lymphoma ([Cheson 2014](#)). If clinical progression is determined by the investigator, radiographic staging should also be performed to determine response assessment per Lugano Classification Revised Staging System for malignant lymphoma. The PET scan metabolic uptake will be graded using the Deauville 5-point scale ([Biggi 2013](#)) ([Barrington 2010](#)) with a score of  $\leq 3$  considered to represent a CmR.

Patients' clinical data must be available for CRF source verification. Copies of tumor images must be made available for review by the sponsor (or its designee), upon request.

### 7.2.2 Part 3

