For patients in Part 3, the determination of antitumor activity will be assessed using the Lugano Classification Revised Staging System for malignant lymphoma ([Cheson 2014](#)) with the incorporation of LYRIC ([Appendix D](#)) ([Cheson 2016](#)). Treatment decisions by the investigator will be based on these assessments. Staging will be performed by PET/CT of diagnostic quality, with disease involvement determined by focal FDG uptake in nodal and extranodal sites (including spleen, liver, bone marrow, and thyroid) that is consistent with lymphoma according to the pattern of uptake and/or CT characteristics. Up to six of the largest nodes, nodal masses, or other involved lesions that are measurable in two diameters

should be identified as target lesions at baseline. If possible, target lesions should be from different regions of the body, and they should include mediastinal and retroperitoneal areas of disease whenever these sites are involved.

At Cycle 2 (Day 15 + 6 days), a CT scan of diagnostic quality will be performed to assess for PD; a limited scan that includes sites of disease identified at baseline is acceptable. For all other response assessments, a clinical response of PD, SD, PR, or CR will be determined unless tumor flare or pseudo-progression is suspected. If tumor flare or pseudoprogression is not suspected, PD is defined by radiological evidence of progression according to the Lugano criteria ([Cheson 2014](#)). If clinical progression is determined by the investigator, radiographic staging should also be performed to determine response assessment per Lugano classification criteria. The PET scan metabolic uptake will be graded using the Deauville 5-point scale ([Barrington 2010](#); [Biggi 2013](#)), with a score of  $\leq 3$  considered to represent a complete metabolic response. Except for the Cycle 2 response assessment, both PET and CT scanning will be required until disease is PET negative; responses will then be followed by CT scan of diagnostic quality only.

If tumor flare or pseudo-progression is suspected by the investigator during treatment, then a clinical response of indeterminate response (IR) will be determined until subsequent evaluation of radiographic imaging or biopsy confirms or refutes PD. IR is defined according to the following:

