### 9.2.2.2 Progression-Free Survival (PFS) after ASCT

PFS after ASCT is defined as the time from ASCT to the first documentation of PD or to death due to any cause, whichever comes first. Patients who do not undergo ASCT will not be included in the analysis of this endpoint. Documentation of PD must be consistent with the criteria described in Section [7.2](#). Specifically, PFS will be calculated as:

$$\text{PFS} = \text{Date of first documented PD or death} - \text{Date of ASCT} + 1.$$

PFS data will be censored as described below:

- Patients who do not have PD and are still on study at the time of an analysis will be censored at the date of the most recent disease assessment prior to the analysis which was adequate to document PD
- Patients who have started an antitumor treatment (excluding high-dose conditioning regimens pre-ASCT, consolidative radiotherapy pre- or post-ASCT, or consolidative treatment with single-agent brentuximab vedotin post-ASCT) other than the study treatment prior to documented PD will be censored at the date of the most recent disease assessment which was adequate to document PD prior to start of new therapy
- Patients who are removed from study prior to documentation of PD will be censored at the date of the most recent disease assessment prior to study discontinuation which was adequate to document PD.

If a patient does not have any adequate disease assessments after ASCT their PFS will be censored at one day.

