#### **9.2.3.2 PFS**

PFS is defined as the time from enrollment to the first documentation of PD or to death due to any cause, whichever comes first. Documentation of PD must be consistent with the criteria described in Section 7.2. Specifically, PFS will be calculated as:

$$\text{PFS} = \text{Date of first documented PD or death} - \text{Date of enrollment} + 1.$$

PFS data will be censored as described below:

- Patients who do not have PD and are still on study at the time of an analysis will be censored at the date of the most recent disease assessment prior to the analysis that was adequate to document PD
- Patients who have started an antitumor treatment (excluding high-dose conditioning regimens pre-ASCT, consolidative radiotherapy pre- or post-ASCT, or consolidative treatment with single-agent brentuximab vedotin post-ASCT) other than the study treatment prior to documented PD will be censored at the date of the most recent disease assessment that was adequate to document PD prior to start of new therapy

- Patients who are removed from study prior to documentation of PD will be censored at the date of the most recent disease assessment prior to study discontinuation that was adequate to document PD.

If a patient does not have any adequate disease assessments after enrollment their PFS will be censored at one day.

An additional exploratory analysis of PFS may be conducted in which clinical assessment will be considered adequate to detect disease progression. Other exploratory analyses of PFS may also be performed. These analyses may involve different definitions of events and/or different censoring rules; details will be provided in the SAP.

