#### **9.3.1.6 Data Transformations and Derivations**

Age in years will be calculated with the SAS INTCK function using informed consent date and birth date.

Study Day will be calculated as Date – First Dose Date + 1 for dates on or after the first dose date. For dates prior to the first dose date, Study Day will be calculated as Date – First Dose Date. For all calculations of Study Day, the First Dose Date will be the earliest date of treatment administration for brentuximab vedotin.

Other time variables based on two dates, e.g., Start Date and End Date, will be calculated as (End Date – Start Date + 1) (in days) unless otherwise specified in the planned analysis section.

The following unit conversion will be implemented unless otherwise specified:

$$\text{Months} = \text{Days} / 30.4375$$

$$\text{Years} = \text{Days} / 365.25$$

Baseline values used in all analyses will be the most recent non-missing measurement prior to the first dose of study drug.

The EOT date will be the date the EOT visit is performed, or 30 days after the last dose of study drug if an EOT visit is not performed.

For efficacy assessments, the date of response will be the latest of all radiologic scan dates for the given disease assessment. The date of progression will be the earliest of all radiologic scan dates for the given restage assessment.

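### The SAP counts a clinical claim without a scan as progression in four endpoints, where the protocol works from scans, and declares no change

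*SAP*

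**What the plan says.** SAP 6.4 sets the rule for efficacy assessments in general. On what counts as PD: "While a radiologic assessment to confirm progression is strongly preferred, an investigator claim of clinical progression is adequate for an assessment of PD". On dating, it keeps the earliest-scan rule and adds an alternative: "or the date of investigator claim of clinical progression".

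Four endpoints take up this rule:

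- PFS after ASCT (SAP 7.5.2.2), by reference to 6.4.
- Duration of CR (7.5.2.3) and duration of OR (7.5.2.4), whose event definitions both include clinical progression as judged by the investigator.
- PFS (7.5.3.2), which takes the earlier date when clinical and radiologic progression are both recorded.

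Protocol Amendment 4 reads differently:

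- Dating (9.3.1.6): "The date of progression will be the earliest of all radiologic scan dates for the given restage assessment". No clinical date is offered.
- Event definition (9.2.3.2, and likewise 9.2.2.2 and 9.2.2.3): "Documentation of PD must be consistent with the criteria described in Section 7.2".
- Section 7.2.2, for Part 3 when flare or pseudoprogression is not suspected: "PD is defined by radiological evidence of progression according to the Lugano criteria".
- Sections 7.2.1 and 7.2.2: "If clinical progression is determined by the investigator, radiographic staging should also be performed to determine response assessment".
- Role of clinical assessment in PFS (9.2.3.2): "An additional exploratory analysis of PFS may be conducted in which clinical assessment will be considered adequate to detect disease progression".

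SAP 9.1 reports no change from the original protocol.

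**The concern.** The protocol treats PFS with clinical assessment as something extra and exploratory. That makes sense only if the main analysis does not count an unscanned clinical claim. The SAP moves such claims into the main analysis of PFS and of all three secondary time-to-event endpoints, and its list of changes is empty.

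SAP 7.5.3.2 also still carries the protocol's exploratory sentence, although its main PFS now does what that sentence offers. The contrast the protocol allowed for has gone. A scan-only version could be run only under a general clause permitting other exploratory PFS analyses.

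At stake is how the main curves are read. The trial is open-label and investigator-assessed, and scheduled CT in follow-up is up to 12 months apart (100 days, then 6, 12, 24 and 36 months; Protocol 6.7). A reader comparing the report with the protocol would not learn how many events rest on a clinical claim alone, or whether they move the estimates.

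**Working it through.** **1. The plan's own figure.** The four endpoints have no design calculation. The only formal one is the CR-rate test (n = 53, reject at 22 or more CRs, 30% vs 50%). The exact binomial gives P(X ≥ 22 | 0.30) = 0.0495 and P(X ≥ 22 | 0.50) = 0.9155, in line with the stated 0.05 and roughly 90%. CR rate is best response before ASCT or new treatment and uses no progression date, so this test is not affected.

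**2. The texts side by side.**

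| Item | Protocol Amendment 4 | SAP |
|---|---|---|
| Progression date | Scan (9.3.1.6) | Scan or clinical claim (6.4) |
| PD in PFS after ASCT | *Must* follow 7.2 (9.2.2.2) | *Should* follow SAP 6.4 (7.5.2.2) |
| PD in duration of CR and OR | Must follow 7.2 (9.2.2.3) | Radiographic or clinical (7.5.2.3, 7.5.2.4) |
| PD in PFS | Must follow 7.2 (9.2.3.2) | Radiologic or clinical, earlier date (7.5.3.2) |
| PFS accepting clinical assessment | Optional, exploratory (9.2.3.2) | Main analysis, yet still listed as exploratory (7.5.3.2) |
| Changes declared | – | None (9.1) |

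**3. Size for one claim with no scan.** All inputs are assumptions: n = 30 or 55 transplanted patients; R radiographic PDs (about 25% or 50% of n) spread as evenly as possible over the CT dates, extras at the earliest dates; one clinical-only claim at month 9, 18 or 30; no deaths and no other censoring. Under the SAP the claim is an event. Under a scan-only rule the patient is censored at the last CT before the claim. With *a* radiographic PDs up to that CT, Kaplan-Meier at month 36 is:

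- SAP: (n − R − 1)/n
- scan-only: [(n − a)/n] × [(n − R − 1)/(n − a − 1)]

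Example, n = 30, R = 8, claim at month 9, a = 4: SAP 21/30 = 70.0%; scan-only 26/30 × 21/25 = 72.8%; difference 2.8 points.

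| n, R | SAP | Scan-only, claim at month 9 / 18 / 30 | Difference (points) |
|---|---|---|---|
| 30, 8 | 70.0% | 72.8 / 73.0 / 73.2% | 2.8 / 3.0 / 3.2 |
| 30, 15 | 46.7% | 48.7 / 49.0 / 49.4% | 2.0 / 2.3 / 2.7 |
| 55, 14 | 72.7% | 74.2 / 74.3 / 74.5% | 1.5 / 1.6 / 1.7 |
| 55, 28 | 47.3% | 48.4 / 48.6 / 48.8% | 1.1 / 1.3 / 1.5 |

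With no clinical-only event the two rules agree.

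**4. Size when a scan follows.** If a claim at month 9 is confirmed by scan at month 10, the event counts under both rules and 36-month PFS is identical. The curves differ only between the two dates, by 1/n: at month 9.5, 83.3% vs 86.7% (n = 30, R = 8) and 87.3% vs 89.1% (n = 55, R = 14).

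**5. More than one claim.** A separate simulation (55 patients, 8 to 16 radiographic PDs by month 24, claims at random times, all assumed) gives a higher scan-only 24-month PFS by about 1.5 to 1.7 points for one clinical-only event, 2.9 to 3.3 for two and 5.8 to 6.6 for four.

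**6. The leftover exploratory sentence.** As an event definition it repeats the main analysis. It could still mean that clinical visits count as adequate assessments for censoring, because SAP 7.5.2.3 and 7.5.2.4 word their censoring in terms of assessments adequate to detect PD. Assumed example: n = 40, two radiographic PDs at each of the five CT dates, two claims at month 8, ten patients last seen at month 9 without a CT.

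- Censored at month 6: 36/40 × 24/26 × 18/24 = 62.3%
- Censored at month 9: 36/40 × 34/36 × 18/24 = 63.75%

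Even so read, it does not give a scan-only result.

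**The case against.** The strongest case is that this is record-keeping. Protocol 9.3 says its plans summarise fuller ones in the SAP, and an amendment is needed only if site conduct changes. The SAP states its rule openly in each relevant section. This stands: the change is permitted. What is missing is its declaration and an analysis showing its effect.

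SAP 9.1 refers to the original protocol, dated 27 May 2015 and not supplied. This also stands. The discrepancy is shown against Amendment 4 only, so 9.1 is not proved false. But SAP 4 describes the amendment that added Part 3, so 9.1 should name its comparator.

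Parts of the protocol are softer than a strict scan rule. For Parts 1 and 2, Section 7.2.1 says PD *includes* radiological evidence and that staging *should* follow a clinical claim. The Part 3 definition is conditional on flare not being suspected. The dating sentence in 9.3.1.6 could be read as a convention for choosing among several scan dates. The firmest conflict is therefore PFS: exploratory in Protocol 9.2.3.2, main in SAP 7.5.3.2. The protocol's contrast was itself optional and limited to PFS, so extending it to all four endpoints goes beyond what the protocol promised.

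The effect may be negligible. Suspected progression prompts a CT (Protocol 6.7; Appendix A, footnote S), and on that path the 36-month difference is 0.0. In the scenarios above, the Wald 95% half-width, 1.96 × √[p(1 − p)/n], is about 12 to 18 points, so a single event lies well within sampling error. These are reasons to call the consequence limited. They do not tell a reader how many such events occurred.

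Clinical-only events might be counted from the submitted data sets if the source of PD is recorded. That is possible, but the SAP does not commit to reporting it.

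**Conclusion.** The concern holds. In four descriptive endpoints the SAP uses a broader definition and dating of PD than Protocol Amendment 4, does not list this as a change, and commits to no analysis that isolates its effect.

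The consequence is limited. None of the four endpoints is formally tested (SAP 6.1). Counting clinical progression is the conservative direction for PFS and duration of response. The CR-rate test and OS are untouched. The 1.1 to 3.2 points per unscanned claim rest wholly on the assumed inputs; the documents do not allow the number of such claims to be derived. The correction should be made because it is cheap and restores a comparison the SAP has lost.

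**What to change.** 1. In SAP 9.1, name the protocol version compared and list the changed PD definition and progression dating.
2. In SAP 7.5.3.2, replace the exploratory sentence with a commitment such as: *A sensitivity analysis of PFS will be performed in which only PD documented radiographically per protocol Section 7.2 is an event, dated by the earliest scan of that restaging (protocol 9.3.1.6).* Alternatively, restore the protocol definition as the main analysis and prespecify the clinical-PD version as the sensitivity analysis.
3. Do the same in 7.5.2.2, 7.5.2.3 and 7.5.2.4, and report the number of clinical-only PD events for each endpoint.
4. If the exploratory sentence was meant as a censoring rule, say so and state which visits count.

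The cost is SAP wording and a few more Kaplan-Meier tables. No new data are needed, provided the source of each PD call (scan or clinical) is recorded. The drawback is that a scan-only analysis censors clinical-only progressors, possibly informatively, and tends to give a higher PFS, so the two versions should be read side by side.
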